3.4. SELECTION OF VISITS

It is possible that more than one visit gets allocated into the same time window. In that case, only one visit will be selected for Tables and figures. The nonselected visit(s) will only be listed and flagged as use=no.

The visit with a relative day (DY) closest to the target day will be selected. If there are multiple visits at the same distance of the scheduled visit day (meaning: equal $ABS(DY - \text{target day})$), then the one latest in time is selected.

In case of an additional screening result, the last pre-baseline measurement is selected as screening value for analysis. This value (not the original screening value) was also used in the clinical center to include the subject in the study.

In case more than one parameter is measured per time point (e.g. for lab), the selection is performed per parameter and per time point, not per “sample” and per time point. Missing values are removed before the selection is made.

A missing baseline value will be imputed with the last nonmissing value of a preceding visit. This can be a screening visit or an unscheduled visit prior to the first dose of study medication; whichever comes latest. If there is no nonmissing result at such screening or unscheduled visits, then the missing baseline value remains missing.

In case the screening visit is used to impute the baseline, the visit will be duplicated in the derived dataset. The original screening visit as well as the imputed baseline will be presented in the tables. In the listings, only original screening data will be shown: the original screening visit will be shown and flagged as “reference” visit. The imputed baseline will not be shown.

In case an unscheduled visit is used to impute the baseline, the visit will be renamed to “baseline” in the derived dataset. The imputed baseline will be presented in the tables. In the listings, the original unscheduled data will be shown and flagged as “reference” visit.

4. HANDLING OF DATA

4.1. CALCULATION OF DESCRIPTIVE STATISTICS

For continuous parameters, descriptive statistics will be presented when $N \geq 2$. When $N=1$, the observation will not be shown in the table but only in the listing.

Descriptive statistics will include at least the following:

- the number of nonmissing data points (N)
- the arithmetic mean
- the standard error (SE)
- the median, minimum and maximum
- 95% confidence interval of the mean (only when requested).

4.2. CALCULATION OF PERCENTAGES

Missing values will not be included in the denominator count when computing percentages.

Imputed missing values are no longer considered to be missing values.

4.3. HANDLING OF VALUES BELOW (OR ABOVE) A THRESHOLD

4.3.1. Safety Data

Values below (above) the detection limit will be imputed by the value of the detection limit itself. Listings will always present the original value.

Example: if the database contains values like “<0.04”, then for the descriptive statistics the value of the detection limit (0.04) shall be used. A value like “>1000” will be imputed by “1000”.

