12.2.3. Number of Significant Digits

The original results and normal limits will be rounded to present only a relevant number of digits. The Mock TLFs contains a table on the expected number of significant digits per lab test. This rounding will be done prior to any parameter derivation. Note that this table also contains the classification of lab tests into categories.

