12.2.4. Baseline and Change from Baseline

The baseline is defined as the last sample prior to first dosing, so should normally be from the Day -1 visit. Baseline will be determined per lab test individually. It is recognized that baseline tests may thus come from more than one lab sample and not just from the “baseline visit” sample.

The change from baseline will be calculated for all post-baseline time points as:

Change from baseline at time point t = value at time point t – baseline value.

The percentage change from baseline will be calculated for all post-baseline time points as:

Percent change from baseline at time point t = 100 x (change from baseline at time point t / baseline value).

Note that the percent change from baseline will be left missing in case the baseline value is zero.

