12.2.5. Scoring of Laboratory Values

12.2.5.1. Scoring according to normal ranges

All values will be compared to their matching normal ranges. The normal ranges provided by the laboratory will be used for this, as available in the database. Values will be scored as abnormally low (L), normal (N) or abnormally high (H).

A value is classified as abnormally low (L) when the value < lower limit of the normal range. A value is classified as abnormally high (H) when the value > upper limit of the normal range. Values equal to the boundaries are still considered normal (N).

An original value like “<X” where X equals the lower limit of the normal range will be classified as abnormally low (L). An original value like “>X” where X equals the upper limit of the normal range will be classified as abnormally high (H).

A normal range of “<10” will be interpreted as: lower limit = 0; upper limit = 10.

A normal range of “>10” will be interpreted as: lower limit = 10; upper limit = +INF.

Tests without normal ranges will not be scored.

Any already existing low/normal/high flags in the raw database will be ignored. The newly derived flag will be used for the analysis TLFs. Any clinical significance flags will be used in the listings.

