Frequency table (with cumulative percentages) per lab test category (hematology, biochemistry, endocrine, urinalysis), lab test, treatment group and time point.

Table for selected tests only.

Population: safety.

Table to be created for the Week 12 interim analysis as well.

Table 14.3.2.10: Laboratory data up to Week 12: Shift table of the ATP III classes per time point

Shift table per lab test category (hematology, biochemistry, endocrine, urinalysis), lab test, treatment group and time point. The table will present the shift in ATP III class at worst-case and last on-treatment (other time points: not needed) versus the baseline class.

Table for selected tests only.

Population: safety.

Table 14.3.2.11: Laboratory data up to Week 12: Treatment-emergent ATP III classes per time point

Frequency table of the treatment-emergent lab ATP III classes per lab test category (hematology, biochemistry), lab test, treatment group and time point (including worst-case). A post-baseline class is considered treatment-emergent if it differs from the baseline result and is of higher category.

Table for selected tests only.

Population: safety.

Table to be created for the Week 12 interim analysis as well.

Table 14.3.2.12: Laboratory data up to Week 12: Frequency table of percent changes from baseline per time point in inhibin B and testosterone

Frequency table of the percent changes from baseline per lab test category (endocrine), lab test, treatment group and time point. The percent changes from baseline will be categorized

as: <-50%, [-50%,+50%], >+50%. A worst-case will also be shown selected as the lowest post-baseline value.

Table only for inhibin B, free testosterone, total testosterone.

Population: safety – males.

Population: safety, selecting male subjects with a baseline value within normal range.

Table to be created for the Week 12 interim analysis as well.

Table 14.3.2.13: Laboratory data up to Week 12: Shift table of the categorical lab data per time point

Shift table per lab test category (hematology, biochemistry, endocrine, urinalysis), lab test, treatment group and time point. Selecting only the tests with categorical data. The table will present the shift in value at each post-baseline time point versus the baseline value.

Population: safety.

12.2.10. Figures up to Week 12

Figure 14.3.2.1: Laboratory data up to Week 12: Mean plots of the actual values over time

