12.2.11. Tables over the whole 24 weeks period

The same tables will be made as for the first period of the study, but with the 5 adapted treatment groups. Time points to present: screening, baseline, Week 1-2-4-8-12, last on-treatment during period 1, worst case during period 1, Weeks 16-20-24, last on-treatment during period 2, follow-up (all follow-up visits in the study), worst case during period 2, last on-treatment during the whole study, worst case during the whole study. Population: Safety.

Table 14.3.2.14: Laboratory data over the whole study: Descriptive statistics of the actual values per time point

Table 14.3.2.15: Laboratory data over the whole study: Descriptive statistics of the changes from baseline per time point

Table 14.3.2.16: Laboratory data over the whole study: Descriptive statistics of the percent changes from baseline per time point

Table 14.3.2.17: Laboratory data over the whole study: Shift table of the lab abnormalities per time point

Table 14.3.2.18: Laboratory data over the whole study: Treatment-emergent lab abnormalities per time point

Table 14.3.2.19: Laboratory data over the whole study: Frequency table of the CTCAE toxicity grades per time point

Table 14.3.2.20: Laboratory data over the whole study: Shift table of the CTCAE toxicity grades per time point

Table 14.3.2.21: Laboratory data over the whole study: Treatment-emergent CTCAE toxicity grades per time point

Table 14.3.2.22: Laboratory data over the whole study: Frequency table of the ATP III classes per time point

Table 14.3.2.23: Laboratory data over the whole study: Shift table of the ATP III classes per time point

Table 14.3.2.24: Laboratory data over the whole study: Treatment-emergent ATP III classes per time point

Table 14.3.2.25: Laboratory data over the whole study: Frequency table of percent changes from baseline per time point in inhibin B and testosterone

Table 14.3.2.26: Laboratory data over the whole study: Shift table of the categorical lab data per time point

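### Rounding aside, a fall in inhibin B or testosterone to below the detection limit L from a detectable baseline at or below 2L is tabulated as within ±50%; that class is not determinable below 2L and wrong at 2L

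*SAP*

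**What the plan says.** SAP 4.3.1 covers safety values outside the detection range: "Values below (above) the detection limit will be imputed by the value of the detection limit itself". Listings keep the original value. SAP 12.2.4 defines percent change from baseline as 100 times the change divided by the baseline value. SAP 12.2.3 rounds results and normal limits to a number of digits held in the separate mock tables, and adds: "This rounding will be done prior to any parameter derivation".

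Table 14.3.2.12 (SAP 12.2.9) is a frequency table of percent changes grouped "as: <-50%, [-50%,+50%], >+50" (per cent). The middle class is closed, so exactly −50% belongs to it. On the extra summary row the SAP says: "A worst-case will also be shown selected as the lowest post-baseline value". On scope: "Table only for inhibin B, free testosterone, total testosterone". The table is made for all men in the safety population and again for men whose baseline was within the normal range. It is also produced for the Week 12 interim analysis.

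Table 14.3.2.25 repeats it over 24 weeks. SAP 12.2.11 states: "The same tables will be made as for the first period of the study, but with the 5 adapted treatment groups".

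The only special rule for a result reported as '<X' is in SAP 12.2.5.1. It concerns low/normal/high scoring when X equals the lower normal limit. The percent-change classes have no such rule.

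**The concern.** An undetectable result says only that the true value is somewhere below L. Setting it to L gives it the largest value it could approach, so every fall to undetectable is scored as small as it could be. For most percent-change summaries that is a tolerable convention. Here the summary is a cut at −50%, and the convention can decide which side of the cut a man falls on.

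The cut has clinical meaning. Protocol 8.3.4 makes two sequential 50% falls in inhibin B or testosterone, with a concurrent rise in FSH or LH respectively, a reason for withdrawal. The risk mitigation text in protocol 6.5 singles out the male reproductive system for attention. Tables 14.3.2.12 and 14.3.2.25 are the only outputs that class hormone change at that cut. If a fall to undetectable is shown in the middle class, the table reports as known something the data do not establish.

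**Working it through.** The plan states no figure on this point, so there is none to reproduce. The check applies the SAP's rules symbolically.

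**Inputs**
- L: the assay's detection limit, assumed the same at both visits. Not given in the documents.
- B: a detectable baseline, so B is at least L.
- V: the true post-baseline value, reported as '<L', so 0 ≤ V < L.
- Imputation V → L from SAP 4.3.1; percent change from SAP 12.2.4; classes from Table 14.3.2.12.
- Rounding under SAP 12.2.3 is set aside at first.

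**Scored change.** 100 × (L − B)/B = 100 × (L/B − 1). This is at or above −50% exactly when L/B ≥ 0.5, that is, when B ≤ 2L.

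**True change.** 100 × (V/B − 1). The true fall is greater than 1 − L/B and at most 100%. It exceeds 50% exactly when V < B/2.

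| B | Scored change | Class shown | True fall | Class shown is |
|---|---|---|---|---|
| 1.2L | −16.7% | within ±50% | 16.7% to 100% | not determinable |
| 1.5L | −33.3% | within ±50% | 33.3% to 100% | not determinable |
| 1.9L | −47.4% | within ±50% | 47.4% to 100% | not determinable |
| 2.0L | −50.0% | within ±50% | above 50% | wrong |
| 2.1L | −52.4% | below −50% | above 52.4% | right |
| 2.5L | −60.0% | below −50% | above 60% | right |

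**Three cases**
- B < 2L: B/2 is less than L, so V may lie on either side of B/2. Both classes are possible, and the table always shows the middle one.
- B = 2L: B/2 equals L, so V < B/2 always holds. The true fall exceeds 50%, but the closed interval puts the scored −50.0% in the middle class.
- B > 2L: scored and true classes agree.

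**Worst-case row.** This takes the lowest post-baseline value. For a man with an undetectable result, that is the imputed L, so the row gives the same class.

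**Rounding.** This can move a result across the boundary in either direction. With L = 1.4 and B = 2.8 rounded to integers, the values become 1 and 3, scored −66.7%, so this B = 2L case is classed correctly by accident. At an assumed one decimal, L = 1.06 and B = 2.24 become 1.1 and 2.2, scored −50.0%, although the true fall is above 1 − 1.06/2.24 = 52.7%. The digits are not in the documents, so the width of the affected zone cannot be stated.

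**The case against.** The strongest objection is that no consequence is shown. Without assay limits or hormone distributions, nothing establishes that any man's baseline lies near or below 2L. In the normal-baseline version of the table the case cannot arise, rounding aside, if the lower normal limit exceeds 2L. This stands, and it limits the weight of the point.

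Second, the example in SAP 4.3.1 speaks of descriptive statistics, and these are frequency tables. The rule's first sentence is general, however, and only listings are exempted. If the rule did not reach these tables, the SAP would have no rule for '<L' in them and a sentence would still be needed. The separate mock tables might hold a display convention; that cannot be checked.

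Third, the information survives elsewhere. Listings keep the original result, and Listing 16.2.11.2 shows each out-of-range value with its baseline. Tables 14.3.1.15 and 14.3.1.30 show events flagged as stopping criteria, and a DSMB reviews safety data. This also stands in large part. Two gaps remain. A man already low at baseline stays low, so Table 14.3.2.5 does not count him as treatment-emergent, although the shift table shows him as low at both times. The interim output comes without listings, although the small-count rule in SAP 6.2 may blank the group columns for a rare class anyway.

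A reader might infer a mirror-image rule for undetectable baselines, with follow-ups above 1.5L always classed correctly. The documents do not support that once SAP 12.2.3 applies: at an assumed one decimal, L = 1.06 with a follow-up of 1.60 becomes 1.1 and 1.6. That scores 1.6/1.1 − 1 = +45.5%, although the true rise exceeds 1.60/1.06 − 1 = 50.9%.

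**Conclusion.** The point holds as a minor one. Rounding aside, a fall to undetectable from a detectable baseline at or below 2L is shown within ±50% in both tables and in their worst-case rows. That class is unsupported below 2L and wrong at 2L. The imputation by itself can only understate such a fall.

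The conclusion rests on reading SAP 4.3.1 as covering these tables and on a common detection limit at both visits. Its size in numbers of men is unknown and may be zero.

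A reader might infer that the tables conceal falls of more than 50%. The documents show that only at B = 2L; below 2L the class shown may be right. Nor do they support a claim that the withdrawal rule is compromised. Nothing in protocol 8.3.4 applies it to imputed values, and the low/normal/high scoring and the listings are likewise unaffected.

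**What to change.** Leave SAP 4.3.1 as it is. For Tables 14.3.2.12 and 14.3.2.25 only, add a rule for post-baseline results reported as '<L' with a detectable baseline:

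1. Compare the reported L and B before rounding.
2. If B is at or above 2L, count the result as below −50%.
3. Otherwise, show it in a separate row labelled 'fell below detection limit, percent change not determinable'.
4. Rank '<L' lowest when selecting the worst case.
5. Keep these men in the denominator. SAP 4.2 removes only missing values, and these results are not missing.

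Imputing half the limit, as SAP 4.3.3 does for pharmacodynamic data, is not a substitute. At B = 1.5L it scores 0.5/1.5 − 1 = −66.7%, which replaces one assumed class with another.

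The cost is a short SAP paragraph, one row and a footnote. The row may be empty. It may include men whose true fall is under 50%: from 1.1L to 0.99L is a 10% fall, which is why the label claims no more than it does. The footnote is needed because these classes may not reconcile with the imputed, rounded percent changes in Tables 14.3.2.3 and 14.3.2.16.

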4.3.2. PK Data

Values below the detection limit will be imputed by a zero.

4.3.3. PD Data

Values below the detection limit will be imputed by half of the value of the detection limit itself. Listings will always present the original value.

4.4. HANDLING MISSING DATA

4.4.1. Handling of Missing Date (Time) or Partially Known Date (Time)

No imputation will be done of missing date (time) fields, nor of the missing parts of partially known date (time) fields. When needed, a worst-case selection will be made. Such worst-case selection rules are elaborated in the specific sections (e.g., AE).

4.4.2. Handling of missing values in scales or summary parameters

Missing items in scales or summary parameters will be imputed to allow for the derivation of the total scale/parameter score. The appropriate imputation rules will be described in the sections where the total scores are defined.

4.4.3. Handling of missing values and early dropouts in the efficacy analyses during the first study period (up to Week 12)

This is for the “efficacy chapter 2” analysis.

For binary data (e.g., ACR20), two different imputations will be done for missing visits as well as early dropouts: non-responder imputation (NRI) and LOCF, up to and including Week 12. The NRI imputation will be primary, and LOCF will be secondary.

For other data (ordinal or continuous), missing visits as well as early dropouts will be imputed using the last observation carried forward (LOCF) algorithm, up to and including Week 12.

Definitions of the imputation methods:

- LOCF (all types of parameters, from binary to continuous): to impute a missing value, the last preceding nonmissing value will be used (which could even be a baseline value).
- NRI (binary response parameters only): to impute a missing response, the subject will be assumed to be a non-responder.

For all parameters, an observed-case analysis will also be performed (i.e., without any imputation). The observed-case analysis will serve as a sensitivity analysis (to ascertain the impact of early dropouts on the results) and will basically be limited to:

- ACR20/50/70/N: descriptive at W12+W24 and inferential at W12
- EULAR remission: descriptive at W12+W24
- SDAI/CDAI: descriptive at BSL+W12+W24
- DAS28: descriptive at BSL+W12+W24 and inferential at W12
- All ACR components (VAS, joint counts, CRP, HAQ-DI): descriptive at BSL+W12+W24
- QoL (FACIT,SF-36): descriptive at BSL+W12+W24.

4.4.4. Handling of missing values and early dropouts in the efficacy analyses during the study period as a whole (full 24 weeks)

This is for the “efficacy chapter 2” analysis.

For binary data (e.g., ACR20), two different imputations will be done for missing visits as well as early dropouts: non-responder imputation (NRI) and LOCF, up to and including Week 24. The NRI imputation will be primary, and LOCF will be secondary.

For other data (ordinal or continuous), missing visits as well as early dropouts will be imputed using the last observation carried forward (LOCF) algorithm, up to and including Week 24.

For all parameters, an observed-case analysis will also be performed (i.e., without any imputation). This observed-case will not be shown for subjects who switched treatment. See previous section for the parts where the observed-case analysis will be presented.

As all subjects in the placebo arm switch to 100 mg q.d. as of Week 12, no placebo arm will be presented during the second part of the study.

4.4.5. Handling of missing values and early dropouts in the efficacy analyses during the second study period (after Week 12)

This is for the “efficacy chapter 3” analysis.

Subjects in this analysis must have data after the Week 12 potential treatment switch in dosing. Subjects who discontinued the study during the first period of the study will not be included in this analysis and will therefore also not be imputed.

For binary data (e.g., ACR20), two different imputations will be done for missing visits as well as early dropouts during period 2: non-responder imputation (NRI) and LOCF, up to and including Week 24. The NRI imputation will be primary, and LOCF will be secondary.

For other data (ordinal or continuous), missing visits as well as early dropouts during period 2 will be imputed using the last observation carried forward (LOCF) algorithm, up to and including Week 24.

Note that no Period 1 efficacy data will be carried forward into this chapter 3 analysis.

For all parameters, an observed-case analysis will also be performed (i.e., without any imputation).

